2.2 Main trial objectives

2.2.1 Clinical aims and objectives

To conduct a multi-centre, randomised trial comparing two commonly used treatments (beta blocker and amiodarone) for NOAF in ICU.

2.2.2 Economic aims and objectives

The economic evaluation will compare beta blocker with amiodarone from a National Health Service (NHS) and Personal Social Services (PSS) perspective. A within-trial cost-effectiveness (CEA) and cost-utility analysis (CUA) will be conducted at 90-days follow up. If the trial demonstrates a difference between strategies, a model-based CUA will extrapolate beyond the endpoint of the trial.

3 TRIAL DESIGN AND SETTING

3.1 Trial design

ABBRUPT is a multi-centre, randomised, controlled open label trial comparing amiodarone with beta blockade for the treatment of NOAF, or a new episode of AF, in the ICU. It will study a total of 2560 patients.

• For the purposes of the trial, NOAF is defined as AF during the acute illness (A&E, deterioration on ward, after surgery) where there is a clinical indication to treat with amiodarone or beta blockers as determined by the attending clinician/ACCP or equivalent.

3.2 Trial setting

At least 60 ICUs across the UK.

3.3 Assessment of risk

All clinical trials can be considered to involve an element of risk and in accordance with the Birmingham Clinical Trials Unit (BCTU) standard operating procedures this trial has been risk assessed to clarify any risks relating uniquely to this trial beyond that associated with usual care. A Risk Assessment has been conducted and concluded that this trial corresponds to the following categorisation:

Type A = No higher than the risk of standard medical care

4 ELIGIBILITY

4.1 Inclusion criteria

- Adult Patients (age ≥16 years)
- Monitored in an area of higher care with the ability to deliver the interventions
- Onset of NOAF, or a new episode of AF, during the acute illness (A&E, deterioration on ward, after surgery) where there is a clinical indication to treat with amiodarone or beta blockers as determined by the attending clinician/ACCP or equivalent.
- Usual electrolyte management with potassium and magnesium has taken place according to site practice

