DSUR	Development Safety Update Report
GCP	Good Clinical Practice
HR	Heart Rate
HRA	Health Research Authority
НТА	Health Technology Assessment Programme
ICF	Informed Consent Form
ICU	Intensive Care Unit
ISF	Investigator Site File
IV	Intravenous
ITT	Intention to Treat

Myocardial infarction
National Health Service
Mean Arterial Pressure
National Institute for Health and Care Excellence
National Institute for Health and Care Research
New-onset atrial fibrillation
Principal Investigator
Patient Information Sheet
Personal Social Services
Quality-adjusted life year
Research Ethics Committee
University of Birmingham Research Governance team
Reference Safety Information
Serious Adverse Event
Statistical Analysis Plan
Serious Adverse Reaction
Summary of Product Characteristics
Suspected Unexpected Serious Adverse Reaction
Trial Master File
Trial Management Group
Trial Steering Committee
University of Birmingham
Women of child-bearing age

TRIAL SUMMARY

Title

A randomised controlled trial to investigate the clinical and cost effectiveness of Amiodarone vs Beta Blockade for new onset atrial fibRillation in icU - a Pragmatic sTudy.

Objectives

To conduct a multi-centre, randomised trial comparing two commonly used treatments (beta blocker and amiodarone) for new onset Atrial Fibrillation (NOAF) in intensive care.

To perform clinical and full economic evaluation to compare treatment with beta blockers and amiodarone.

Trial design

Open-label interventional multi-centre two-arm randomised controlled trial with internal pilot and economic evaluation.

Patient population and sample size

Patients (≥16 years) requiring a high level of care with NOAF or a new episode of AF within this acute admission for which therapeutic intervention with either beta blockers or amiodarone is planned by the clinical team. In total, 2560 patients (1280 per arm) will be randomised.

Setting

Critical care units in NHS Trusts/ Health Boards within the UK

Eligibility criteria

Inclusion criteria

- Adult Patients (age ≥16 years)
- Monitored in an area of higher care with the ability to deliver the interventions
- Onset of NOAF or a new episode of AF during the acute illness (A&E, deterioration on ward, after surgery) where there is a clinical indication to treat with amiodarone or beta blockers as determined by the attending clinician/ACCP or equivalent.
- Usual electrolyte management with potassium and magnesium has taken place according to site practice

Exclusion criteria

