7 TRIAL INTERVENTION

7.1 Trial interventions and dosing schedule

Patients will be randomised to either the intervention group (amiodarone) or the control group (beta-blockade). For the purposes of the trial, amiodarone and beta-blockers are defined as Investigational Medicinal Products (IMPs)

For those patients randomised to the intervention group, amiodarone will be prescribed according to the local treatment pathway and practice for AF. The treating clinician choosing the route of administration, dose and duration in accordance with local practice.

For those patients randomised to the control group, clinicians will prescribe the beta-blocker which aligns with their local treatment pathway and practice for AF. The beta-blocker choice should reflect local availability and familiarity. They may be administered enterally or intravenously; dosing should be according to local practice.

Patients will be treated with the allocated intervention until sinus rhythm has been maintained for 24 hours. Clinicians should then consider stopping the intervention according to local practice.

Compliance for ICU patients will be assessed from the observation and medication charts. The dosage of the intervention (amiodarone or beta-blocker) will be recorded up until Day-7 on the corresponding case report form (CRF).

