8.2 Main trial outcomes

Primary outcome

90-day mortality

Secondary outcomes

Clinical Outcomes

- ICU and hospital mortality
- Rates of Cardiovascular events including stroke, myocardial infarction or thromboembolism at 90-days
- Rate of established AF by the end of ICU stay / death/ day 90

Economic Outcomes

- Cost-effectiveness of the interventions
- · Health care resource use including ICU and hospital length of stay

Safety Outcomes

- The number episodes of bradycardia (HR <50 bpm) whilst in hospital and being prescribed the intervention
- Bradycardia and bradycardic arrhythmias with haemodynamic compromise requiring intervention
- Significant hypotension requiring intervention (not including temporarily stopping the trial medication) whilst in ICU
- Heart block
- Arrhythmia with haemodynamic compromise requiring intervention including DC cardioversion

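### Significant hypotension counts only in ICU, although eligibility does not require ICU and trial drug may continue after it; the care-location wording needs reconciling

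*Protocol*

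**What the plan says.** **Who may enter.** Inclusion (4.1) requires the patient to be "Monitored in an area of higher care with the ability to deliver the interventions". The term is not defined and ICU admission is not a criterion. The Trial Summary likewise describes patients "requiring a high level of care with NOAF or a new episode of AF within this acute admission".

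**Where the trial is set.** Section 3.1 describes treatment of AF in the ICU. Section 3.2 gives the setting as "At least 60 ICUs across the UK". Section 9 asks for the ICU admission date at randomisation and has an ICU-discharge visit.

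**What is measured (8.2).** Four entries refer to ICU:
- "ICU and hospital mortality", which 16.4 analyses as time-to-event by the primary-outcome methods;
- "Rate of established AF by the end of ICU stay / death/ day 90";
- "Significant hypotension requiring intervention (not including temporarily stopping the trial medication) whilst in ICU";
- ICU length of stay, within resource use.

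Episodes of bradycardia below 50 bpm have a different window: the hospital stay, for as long as the allocated drug is prescribed. The other three safety outcomes carry no location limit.

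**How long treatment lasts.** Section 7.6 expects both drugs to stop at ICU discharge but allows them to continue where clinically indicated. Section 9 records ongoing use of either study drug at ICU discharge, hospital discharge, Day 60 and Day 90.

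**Who is analysed.** Section 16.2 sets intention to treat for all analyses.

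**The concern.** The eligibility text and the outcome text are anchored to different places. Eligibility decides who can be randomised, and it is the wider of the two. A patient can satisfy 4.1 and never enter ICU, enter ICU only after randomisation, or have left ICU for another monitored area before randomisation. The protocol has no rule for any of these.

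The hypotension outcome has a second problem, which remains even if every patient is in ICU at randomisation. Its window closes when the patient leaves ICU, while treatment may go on. The window's length is therefore set by ICU length of stay, which the allocated drug may affect, in a trial where clinicians know the allocation (6.6). The protocol itself flags blood pressure for both arms: 7.2 lists a fall in blood pressure among the common effects of amiodarone, and 7.3 warns of marked hypotension when beta blockade is combined with certain agents. What is at stake is a complete and even count of a safety event that bears directly on the comparison.

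**Working it through.** **1. The primary outcome is not touched.** It is death from any cause, timed from randomisation (16.3), so care location plays no part. The sample size in 16.1 reproduces:
- HR = ln(0.85)/ln(0.80) = 0.728.
- Freedman's formula, two-sided 0.05 and 90% power, gives 426 events.
- 426/0.175 = 2434, stated as about 2430.
- 2430/0.95 = 2558, rounded to 2560.

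**2. Each ICU-based outcome for a patient not in ICU at randomisation.**

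| Outcome (8.2) | Never in ICU after randomisation | ICU only after randomisation |
|---|---|---|
| ICU mortality | no window, no rule | window opens after treatment starts |
| Hypotension | no window, cannot be counted | earlier on-drug events not counted |
| ICU length of stay | could be set to zero, but no rule says so | defined, starts late |
| Established AF | ICU time point absent; death and Day 90 remain | ICU time point comes later |

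**3. The two safety windows side by side.**

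| | Bradycardia episodes | Significant hypotension |
|---|---|---|
| Location | hospital | ICU |
| Tied to being on drug | yes | no |
| On-drug event after ICU discharge | counted | not counted |

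Treatment may continue after ICU (7.6), so the last row can occur for patients who were in ICU throughout their early treatment. It needs no assumption about where patients are randomised.

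In 16.4 only count outcomes get a time offset. Hypotension is not worded as a count. If it is analysed as binary, nothing adjusts for unequal ICU time.

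**4. How large could a spurious difference be?** The protocol does not give the share randomised outside ICU, so the inputs below are assumptions. Let s be that share, a the proportion of them later admitted to ICU, and r the true hypotension risk, equal in both arms. If hypotension is recorded only for patients who reach ICU:

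recorded risk = r × [(1 − s) + s × a]

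Example with r = 30%, s = 20%, a = 40% versus 30%:
- 0.30 × (0.80 + 0.08) = 26.4%
- 0.30 × (0.80 + 0.06) = 25.8%
- relative risk = 26.4/25.8 = 1.023

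| s | Patients of 2560 | RR, a = 40% v 30% | RR, a = 50% v 30% |
|---|---|---|---|
| 5% | 128 | 1.005 | 1.010 |
| 10% | 256 | 1.011 | 1.022 |
| 20% | 512 | 1.023 | 1.047 |
| 30% | 768 | 1.038 | 1.076 |

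The true risk r cancels from the ratio. With equal later admission, or with s = 0, the ratio is exactly 1.

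**5. What cannot be sized.** The protocol gives neither the share continuing treatment after ICU nor the expected ICU stay by arm. The number of on-drug hypotension events lost after ICU discharge (step 3) therefore cannot be calculated.

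**The case against.** The strongest reply is that this is an ICU trial. Sections 1.3, 3.1 and 3.2 place it there, section 5 expects nearly all patients to be sedated and ventilated, and section 9 records an ICU admission date. On that reading the higher-care criterion simply means critical care. This makes it likely that most patients will be in ICU. It does not narrow 4.1, and it leaves the post-ICU gap in the hypotension window untouched.

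A reader might infer more than the documents support:

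- **That patients will be randomised in A&E or on wards.** The locations in "during the acute illness (A&E, deterioration on ward, after surgery" say where the AF arises, not where randomisation takes place.
- **That the AF outcome is undefined.** It also names death and Day 90, and section 9 lists AF resolution at hospital discharge, Day 60 and Day 90. One time point is ambiguous; the outcome is not lost.
- **That compliance is assessed only in ICU**, from "Compliance for ICU patients will be assessed from the observation and medication charts". Section 7.7.4 documents adherence in both arms from the medical notes without an ICU limit.
- **That scoring never-ICU patients as event-free biases the comparison.** With 20% outside ICU in each arm, a 20% risk becomes 0.8 × 20% = 16% in both, and the relative risk is unchanged. Bias needs ICU admission or ICU stay to differ by arm.
- **That hypotension outside ICU goes unrecorded.** Section 9 collects mean arterial pressure and vasopressor or inotrope doses on Days 0 to 3 and Day 7. Section 11.6 puts cardiovascular failure on the follow-up forms, and SAEs run for 90 days. These data do not form the named outcome, and the scheduled pressure readings stop at Day 7.

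It is also fair that a statistical analysis plan may give rules for patients without an ICU stay, and that the list of forms in 12.2 is not exhaustive, so a location field may exist. However, eligibility and the outcome windows are fixed in the protocol, and a care location that was never collected cannot be recovered at analysis.

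**Conclusion.** The point holds as an inconsistency between eligibility and outcome definitions, and as a badly chosen window for one safety outcome. The hypotension part stands whatever the share outside ICU: following 8.2 as written omits on-treatment hypotension outside ICU, and the length of the window depends on something that happens after randomisation. The ICU mortality part applies only to patients not in ICU at randomisation, whose number is unknown and could be zero.

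Where the distortion from care location at entry can be illustrated, it is small: relative risks of 1.005 to 1.076, and none if all patients are in ICU at entry. Those figures rest entirely on assumed shares and assumed differences in later admission. The effect of the post-ICU gap has no figure. Only secondary, safety and economic outcomes are involved. The change is worth making because it is cheap and hypotension is a named safety outcome in an open-label comparison.

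**What to change.** 1. **Hypotension window (8.2).** Count hypotension requiring intervention over the same window as bradycardia, or over a fixed period from randomisation.
2. **Wording (3.1, 3.2, 4.1, 8.2).** Define the higher-care area and ICU once and reconcile the four sections. State whether ICU in the outcomes includes the higher-care area where the patient was randomised. Which population is meant is for the trial team to say.
3. **Data and analysis.** Record care location at randomisation if no form does so already, and keep all randomised patients in these analyses, in line with 16.2.

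The cost is a few lines of protocol text and one data field. The one real burden is that sites must also extract hypotension from ward or high-dependency records for the chosen window. Under the bradycardia window, sites already have to review hospital records while the patient is on trial drug.

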4.2 Exclusion criteria

- Treatment with anticoagulants or antiarrhythmics for the treatment of AF before the current hospital admission *anticoagulants or antiarrhythmics used for any other purpose can be included
- Current concomitant medication that are contraindicated with the intervention / comparator medications (e.g. Ciclosporin, Itaconazole, Letermovir)
- Serum Potassium of < 4 mmol ^{L-1} (measured either on Point-of-Care Testing or Laboratory)
- Patients having undergone cardiac surgery during the current hospital admission, defined as any surgery including lung resections, stent procedures such as percutaneous coronary interventions or other angioplasty procedures done on the heart muscle, valves or thoracic arteries including the thoracic part of the aorta
- Thyrotoxicosis
- Withdrawal of life support therapy within 24 hours
- Any other known contraindication or known sensitivity to beta-blockers or amiodarone
- Known pregnancy or patients currently known to be breast-feeding

4.3 Confirmation of eligibility

The Medicines for Human Use (Clinical Trials) Regulations state that 'the decision whether a subject is eligible for entry into a clinical trial is considered to be a medical decision and must be made by a medically qualified doctor the medical care given to, and medical decisions made on behalf of, subjects shall always be the responsibility of an appropriately qualified doctor or, when appropriate, of a qualified dentist' (Part2 (11) of Schedule 1 to SI 2004/1031). However, within the critical care setting, the role of Advanced Critical Care Practitioners (ACCPs) or equivalent e.g. Advanced Nurse Practitioners (ANPs), Clinical Nurse Specialists (CNSs) have developed into autonomous practitioners; their skills include non-medical prescribing, assessment, diagnosis and the management of patients' health needs and complex clinical decision making. (26)

Thus, it is appropriate in ABBRUPT (as a Type A CTIMP) to take a risk proportionate approach to the assessment of eligibility. Confirmation that a patient is eligible to be randomised into ABBRUPT may be confirmed by either a medically qualified doctor or an ACCP (or equivalent), working under the supervision of a medically qualified doctor. In all instances, those confirming eligibility must be trained on the ABBRUPT trial procedures and have been delegated the task of confirming eligibility by the PI, either by being added to the delegation log or by being provided with the link to the eligibility and

randomisation training by the PI. The name of the person who has confirmed eligibility will be recorded in the patient's medical notes and will also be captured on the Randomisation Form.

4.4 Co-enrolment

The Trial Management Group (TMG) will consider requests for co-enrolment into other trials in accordance with best practice recommendations (27). Co-enrolment to other trials will be considered on a case-by-case basis by the ABBRUPT TMG. Prior to co-enrolment being agreed, the following will be reviewed and considered: study design and statistical considerations; legal and ethical considerations; biological and scientific rationale; patient considerations and logistical and organisational issues. Co-enrolment to Clinical Trials of Investigational Medicinal Products (CTIMPs), will be restricted to those assessed to be 'Type A' that are comparable to the risk of standard medical care, where the intervention(s) would commonly be used in the treatment of the patient, and where no biological interactions or additional safety reporting will be required for concomitant administration of the intervention(s).

For co-enrolment to occur, an agreement will be reached between the respective trials team prior to the patient being considered for inclusion. A log of all patients co-enrolled will be maintained by the ABBRUPT Trial Office.

5 CONSENT

It is the responsibility of the Principal Investigator (PI) to obtain written informed consent for each patient. This task can be delegated by the PI to other members of the local research team, if local practice allows and this responsibility has been documented in the site signature and delegation log.

NOAF can be a life-threatening condition requiring urgent treatment. The vast majority of eligible patients will be sedated and mechanically ventilated and will therefore lack capacity to consent for themselves. Furthermore, owing to the need for urgent treatment, it would be clinically unjustifiable to delay treatment until informed consent can be obtained from a legal representative. Even if such a representative were immediately available, the emotional distress of the situation is such that they would be unlikely to make an informed decision in the minimal time available. Consequently, ABBRUPT cannot be conducted on the basis of prospective informed consent.

Patients who are incapable of giving consent in emergency situations are an established exception to the general rule of informed consent in clinical trials. This is clearly acknowledged in the Declaration of Helsinki 2008. Under UK law, emergency care is permitted under the terms of The Medicines for Human Use (Clinical Trials; Amendment No.2) Regulations 2006. Specifically:

- Having regard to the nature of the trial and the particular circumstances of the case, it is necessary to take action for the purpose of the trial as a matter of urgency
- It is not reasonably practicable to obtain informed consent prior to entering the subject
- The action to be taken is carried out in accordance with a procedure approved by the research ethics committee

5.1 Patient consent (after trial intervention)

An assessment will be made at site to determine whether the patient has regained capacity and is able to consent for themselves. Where this is found to be the case, a Patient Information Sheet (PIS) will be provided to facilitate this process. The PI or delegate will ensure that they adequately explain the aim of the trial, the trial intervention, and the anticipated benefits and potential hazards of taking part in the trial to the patient. They will also explain that their continued participation is voluntary and that they are free to decide to withdraw from the trial at any time. The patient will be given adequate time to read, or have read to them, the PIS and to discuss their participation with others outside of the site research team. The patient will also be given the opportunity to ask questions before signing and dating the latest version of the Informed Consent Form (ICF). If the patient then confirms that they are willing to continue participating in the trial, they will be asked to sign and date the latest version of the ICF. The PI or delegate will then sign and date the ICF. Where a patient is physically unable to sign the ICF, a witness will be able to sign on their behalf. A copy of the ICF will be given to the patient, a copy will be filed in the medical notes and the original placed in the Investigator Site File (ISF). The patient's trial number will be entered on the ICF. In addition, the patient will be asked to confirm that they understand that a copy of the signed ICF will be transferred to BCTU for review.

Details of the informed consent discussions will be recorded in the patient's medical notes. This will include date of discussion, the name of the trial, summary of discussion, version number of the PIS given to the patient, version number of ICF signed and date consent received.

Throughout their participation in the trial, the patient's willingness to continue in the trial will be ascertained and documented in the medical notes. The patient will have the opportunity to ask questions about the trial. Any new information that may be relevant to the patient's continued participation will be provided. Where new information becomes available which may affect the patient's decision to continue, they will be given time to consider and if happy to continue they will

be re-consented. Re-consent will be documented in the medical notes. The patient's right to withdraw from the trial will remain.

Electronic copies of the PIS and ICF will be available from the ABBRUPT Trial Office and these should be presented on the headed paper of the site.

